# 13 DATA HANDLING AND ADMINISTRATIVE REQUIREMENTS

## 13.1 Subject Confidentiality

The investigator must ensure that the subject's identity is kept confidential throughout the course of the study. In particular, the investigator must keep an enrollment log with

confidential identifying information that corresponds to the subject numbers and initials of each study participant. The study sponsor may collect a copy of the enrollment log **without any directly identifying subject information**.

The study sponsor may share patient-level data collected in this trial with qualified researchers to help facilitate product development or enhancements in research that is not directly related to the study objectives. The Informed Consent explains this to the study subject.

## 13.2 Completion of Source Documents and Case Report Forms

The nature and location of all source documents will be identified to ensure that original data required to complete the CRFs exist and are accessible for verification by the site monitor, and all discrepancies shall be appropriately documented via the query resolution process. Site monitors are appointed by the study sponsor and are independent of study site staff.

If electronic records are maintained, the method of verification must be determined in advance of starting the study.

At a minimum, source documents include the following information for each subject:

- Subject identification (name, sex, race, ethnicity, age)
- Documentation of subject eligibility
- Date of informed consent
- Dates of visits
- Documentation that protocol specific procedures were performed
- Results of study parameters, as required by the protocol
- IP accountability records
- Documentation of AEs and other safety parameters (if applicable)
- Records regarding medical histories and the use of concomitant therapies prior to and during the study
- Date of study completion and reason for early discontinuation, if applicable

It is required that the author of an entry in the source documents be identifiable. Direct access to source documentation (medical records) must be allowed for the purpose of verifying that the data recorded on the CRF are consistent with the original source data.

Only designated individuals at the site will complete the CRFs. The CRFs must be completed at regular intervals following the clinical study visit schedule. It is expected that all data reported have corresponding entries in the source documents. The principal investigator is responsible for reviewing and certifying that the CRFs are accurate and complete. The only subject identifiers recorded on the CRFs will be subject number, and subject demographic information.

### **13.3 Data Review and Clarifications**

A review of CRF data to the subject's source data will be completed by the site monitor to ensure completeness and accuracy. After the CRFs have been completed, additional data clarifications and/or additions may be needed as a result of the data cleaning process. Data clarifications are documented and are part of each subject's CRF.

### **13.4 Sponsor and Monitoring Responsibilities**

The study sponsor will select principal investigators that are qualified by education, training, and experience to assume responsibility for the proper conduct of this clinical trial. For this study, the principal investigator must be a health care professional licensed to perform cataract surgery.

[figure not shown]
The study sponsor is financially funding this clinical trial and will compensate the investigator and/or the Institution(s) at which the study is conducted in accordance with a signed clinical trial agreement.

The study sponsor will designate a monitor to conduct the appropriate site visits at the appropriate intervals according to the study monitoring plan. The clinical investigation will be monitored to ensure that the rights and well-being of the subjects are protected, the reported data are accurate, complete, and verifiable from the source documents, and the study is conducted in compliance with the current approved protocol (and amendments[s], if applicable), with current GCP, and with applicable regulatory requirements.

The site may not screen subjects or perform the informed consent process on any subject until it receives a notification from an appropriate study sponsor representative that the site may commence conducting study activities. Monitoring will be conducted periodically while the clinical study is ongoing. Monitoring methods may include site visits, telephone, written, and fax correspondence. Close-out visits will take place after the last visit of the last subject at the site.

Videos of surgery should be maintained with subject records for verification as source data and sent to sponsor for review as requested. Such data will be coded with a subject number only and will not contain subject personal information.

A coordinating investigator may be identified by the study sponsor to review and endorse the final study report. In cases where a coordinating investigator is engaged, the study sponsor will select the coordinating investigator based upon their experience, qualifications, active study participation, and their willingness and availability to take on this role.

### **13.5 Regulatory Documentation and Records Retention**

The investigator is required to maintain up-to-date, complete regulatory documentation as indicated by the study sponsor and the investigator's files will be reviewed as part of the ongoing study monitoring. Financial information is to be kept separately.

Additionally, the investigator must keep study records and source documents consistent with the terms of the clinical study agreement with the study sponsor. If the investigator retires, relocates, or for any other reason withdraws from responsibility of keeping the study records, then the study sponsor must be notified, and suitable arrangements made for retention of study records and source documents needed to comply with national and international regulations.

### **13.6 Quality Assurance and Quality Control**

The study sponsor will secure agreement from all involved parties to ensure direct access to all study related sites, source data and documents, and reports for the purpose of monitoring

and auditing by the study sponsor, and inspection by domestic and foreign regulatory authorities. Quality control will be applied to each stage of data handling to ensure that all data are reliable and have been processed correctly. Agreements made by the study sponsor with the investigator/institution and any other parties involved in the clinical study will be provided in writing as part of the protocol or as a separate agreement.

## 14 ETHICS

Investigations are conducted in compliance with Good Clinical Practices; international and national regulations, laws and guidelines; ISO 14155; the conditions of approval imposed by reviewing IRBs/IECs or regulatory authorities; and in accordance with the ethical medical research principles outlined in the Declaration of Helsinki.

- The SOPs of the study sponsor and contract research organizations participating in the conduct of the clinical study and all other applicable regulations shall apply.
- Notifications and timelines for reporting protocol deviations should be based upon applicable IRB/Ethics Committee requirements.

The investigator must ensure that all personnel involved in the conduct of the study are qualified to perform their assigned responsibilities through relevant education, training, and experience. The investigator and all clinical study staff must conduct the clinical study in compliance with the protocol. The investigator is not allowed to deviate from the protocol except to protect the rights, safety, and well-being of human subjects under emergency circumstances. Emergency deviations may proceed without prior approval of the sponsor and the IRB/IEC but shall be documented and reported to the sponsor and the IRB/IEC as soon as possible. Deviations from this protocol, regulatory requirements, and/or GCP must be recorded and reported to the Sponsor prior to database lock. If needed, corrective and preventive action should be identified, implemented, and documented within the study records. Failure to implement identified corrective and preventative actions may result in site closure by the sponsor. Use of waivers to deviate from the clinical protocol is prohibited.

Before clinical study initiation, this protocol, the informed consent form, if applicable, any other written information given to subjects, and any advertisements planned for subject recruitment must be approved by an IRB/IEC. The investigator must provide documentation of the IRB/IEC approval to the study sponsor. The approval must be dated and must identify the applicable protocol, amendments (if any), informed consent form, assent form (if any), all applicable recruiting materials, written information for subject, and subject compensation programs. The IRB/IEC must be provided with a copy of the Investigator's Brochure, any periodic safety updates, and all other information as required by local regulation and/or the

IRB/IEC. Any additional requirements imposed by the IRB/IEC or regulatory authority shall be followed. At the end of the study, the investigator must notify the IRB/IEC about the study's completion. The IRB/IEC also must be notified if the study is terminated prematurely. Finally, the investigator must report to the IRB/IEC on the progress of the study at intervals stipulated by the IRB/IEC.

Voluntary informed consent must be obtained in writing from every subject. The obtaining of consent shall be documented before any procedure specific to the clinical investigation is applied to the subject.

The investigator must have a defined process for obtaining the required consent. Specifically, the investigator, or their delegate, must explain the clinical study to each potential subject and the subject must indicate voluntary consent by signing and dating the approved informed consent form. The subject must be provided an opportunity to ask questions of the investigator, and if required by local regulation, other qualified personnel. The investigator must provide the subject with a copy of the consent form written in a language the subject understands. The consent document must meet all applicable local laws and provide subjects with information regarding the purpose, procedures, requirements, and restrictions of the study, along with any known risks and potential benefits associated with the IP and the study, the available compensation, and the established provisions for maintaining confidentiality of personal, protected health information. Subjects will be told about the voluntary nature of participation in the study and must be provided with contact information for the appropriate individuals should questions or concerns arise during the study. The subject also must be told that their records may be accessed by appropriate authorities and sponsor-designated personnel. The investigator must keep the original, signed copy of the consent (file in subject's medical records) and must provide a duplicate copy to each subject according to local regulations.

The investigator must have a defined process in case a subject would like to withdraw their consent(s). The investigator is the designated contact point for any such withdrawals.

The investigator must have a defined process in case a subject would like to exercise any of their rights under applicable Data Protection laws. The investigator is the designated contact point for any such requests.

The sponsor will secure a human clinical trial insurance certificate according to applicable country regulations when required.

The study sponsor assures that the key designs of this protocol will be registered on public databases where required by current regulations, and, as applicable, results will be posted.

**Executive Summary:**

**Key Objectives:**

The objective of this study is to obtain device-specific safety and performance clinical data to support marketability in Europe, and to collect user preference data.

## 1 STUDY OBJECTIVES AND DESIGN

### 1.1 Study Objectives

The study objectives are to obtain device-specific safety and performance clinical data to support marketability in Europe, and to collect user preference data.

### 1.2 Study Description

This is a prospective, interventional, open-label, single-arm, nonrandomized, multicenter clinical study in the United States of America (USA) and/or Australia with approximately a 1-month follow-up. The investigational product is the UNITY Vitreoretinal Cataract System (VCS). The target patient population for this study are adults undergoing anterior segment ophthalmic surgery who meet the inclusion/exclusion criteria.

The UNITY Vitreoretinal Cataract System (VCS) consisting of the console and compatible devices, is intended to facilitate management of fluid and gases, as well as removal, grasping, cutting, illumination and coagulation of ocular materials. The UNITY VCS, consisting of the console and compatible devices, is indicated for use during anterior and posterior segment ophthalmic surgery, however, only the anterior segment functionalities will be enabled during this study. Approximately 120 subjects will be enrolled, and 100 subjects are expected to complete the study. Up to 5 study sites will participate in this clinical study and will be located in the United States and/or Australia.

Planned study visits will include screening/enrollment, cataract surgery using UNITY VCS, follow-up at 1 day, 1 week, and 1 month. Screening fail/early exit visits will be included as appropriate.

The schedule of study procedures and assessments can be found in the appendix.

### 1.3 Randomization

There will be no randomization of subjects.

If both eyes qualify for the study, the study eye will be determined per investigator's discretion.

### 1.4 Masking

This is an open-label study.

## 1.5 Interim Analysis

No interim analyses are planned for this study.

## 2 ANALYSIS SETS

All eligible subjects will be screened to determine if they meet all inclusion and no exclusion criteria. Subjects who provide informed consent will be considered enrolled in the study.

### 2.1 All-Implanted Analysis Sets

The primary analysis set for effectiveness outcomes will be the all-implanted analysis set. The all-implanted analysis set includes all eyes with successful completion of the cataract surgery, including IOL implantation.

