	

• Diagnosed with severe systemic (e.g., history of cerebral vascular accident) or retinal disorders (e.g., macular degeneration, diabetic retinopathy, or other retinal pathology that might limit postoperative visual acuity or predispose the subject to postoperative retinal complications) in the operative eye

• A poorly dilating pupil or other pupil defect that prevents the iris from retracting peripherally to at least 6 mm diameter dilation in the operative eye

Data analysis and sample size justification	
The primary analysis set for effectiveness outcomes will be the all-implanted analysis set. The all-implanted analysis set includes all eyes with successful completion of the cataract surgery including IOL implantation. The safety analysis set will include all eyes with attempted use of the UNITY VCS (successful or aborted after contact with the eye) and will be used for the safety outcomes. Attempted use of the UNITY VCS is defined as any time the device makes contact with the eye.
 
There will be no hypothesis testing for any study outcome. All study outcomes will be presented as data listings or with summary statistics that are appropriate to the scale of the endpoint (continuous, dichotomous, etc.).
 
Based on a sample of 100 subjects, the expected half-width of the 95 % confidence interval for the percentage of surgeons reporting 'yes' to the question "Did UNITY VCS using anterior segment surgical functionality perform per the intended use as defined in Protocol Section 5.1?" will be <math>1.96 \cdot \sqrt{(p(1-p)/100)}</math>. This half-width is widest at <math>p = 50\%</math>. Under this conservative assumption, the expected half-width is <10% given the sample size of 100.
 
Allow enrollment for an additional 10% for screen failure and 10% for lost to follow-up to ensure 100 completed subjects.

**Table 3–1** Schedule of Study Procedures and Assessments

Visit	Visit 0 Screening	Visit 00 Surgery	Visit 1 1 Day	Visit 2 1 Week	Visit 3 1 Month / Exit	Early Exit	Unscheduled Visit 
Day Number	Day -60 to 0	Day 0	Day 1 to 3	Day 4 to 10	Day 28 to 42	N/A	N/A
Eye	Both Eyes	Study eye	Study eye	Study eye	Study eye	Study eye	Study eye
Informed Consent	X						
Demographics	X						
Medical and Ocular History	X						
Concomitant Medications	X	X	X	X	X	X	X
Inclusion/Exclusion	X						

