### **12.2.1 All-Implanted Analysis Set**

The primary analysis set for effectiveness outcomes will be the all-implanted analysis set. The all-implanted analysis set includes all eyes with successful completion of the cataract surgery, including IOL implantation.

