### 2.2 Safety Analysis Set

The safety analysis set will include all eyes with attempted use of the UNITY VCS (successful or aborted after contact with the eye) and will be used for the safety outcomes. Attempted use of the UNITY VCS is defined as any time the device makes contact with the eye.

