## 3 SUBJECT CHARACTERISTICS AND STUDY CONDUCT SUMMARIES

Subject characteristics and study conduct summaries will include subject disposition, demographics, and baseline cataract grade. Listings will be provided for medical history, screen failures by reason, protocol deviations, baseline medications, and for subjects included in the Safety analysis set but excluded from the All-Implanted analysis set. All descriptive summary statistics will be displayed with count and percent for categorical data, and with sample size (N), mean, standard deviation, median, minimum, and maximum for continuous data.

Subject characteristics and study conduct summaries will be presented for the all-implanted analysis set unless the safety analysis set is different, in which case they will be presented for both.

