### 4.1 Effectiveness Endpoints:

Primary Endpoint

- From the surgeon questionnaire, which is completed after each subject surgery, the percentage of 'Yes' responses to the question: ***Did UNITY VCS using anterior segment surgical functionality perform per the intended use as defined in Protocol Section 5.1?***

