### 4.3 Statistical Methods for Effectiveness Analyses

[figure not shown]
Standard descriptive statistics will be presented based on the type. Individual subject data listings will also be provided. No imputation of missing data is planned. The all-implanted analysis set will be used for all effectiveness analysis and all analyses will be based on the study eye unless otherwise stated.

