#### 4.3.1 Analysis of the Primary Endpoint

After each surgery, the surgeon completes a user preference questionnaire. For subjects in the all-implanted analysis set, the rate of 'Yes' responses to the question ***Did UNITY VCS using anterior segment surgical functionality perform per the intended use as defined in Protocol Section 5.1?*** will be presented with a count and percentage and will be accompanied by a two-sided exact binomial 95% confidence interval.

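### The primary 'performed per intended use' rate leaves out attempted eyes whose surgery was not completed, so it is likely biased upward

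*SAP*

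**What the plan says.** SAP 2.1 defines the set: "The all-implanted analysis set includes all eyes with successful completion of the cataract surgery, including IOL implantation". Protocol 12.2.1 and the summary in Protocol Section 3 carry the same definition, and Protocol 12.2.1 gives it the leading role: "The primary analysis set for effectiveness outcomes will be the all-implanted analysis set".

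SAP 4.3 applies it throughout: "The all-implanted analysis set will be used for all effectiveness analysis". SAP 4.3.1 repeats this for the primary endpoint, "For subjects in the all-implanted analysis set, the rate of" 'Yes' answers, reported as a count and percentage with a two-sided exact binomial 95% confidence interval. The answers come, per SAP 4.1, "From the surgeon questionnaire, which is completed after each subject surgery".

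A wider set exists. SAP 2.2 states: "The safety analysis set will include all eyes with attempted use of the UNITY VCS (successful or aborted after contact with the eye"). It is used for safety outcomes only. SAP 3 plans a listing "for subjects included in the Safety analysis set but excluded from the All-Implanted analysis set". The available text has no primary rate in the wider set.

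**The concern.** The question is whether the device did its job, but eyes enter the denominator only if the operation ended successfully with a lens in place. That is an outcome arising after the device is used, and the device can influence it. A device failure that stops surgery removes that eye from the result instead of counting against it.

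The set also does not match the endpoint. Protocol 5.1 limits the device's purpose in this study to fluid management and to removing, cutting and coagulating ocular material. Implanting the IOL is not among these functions, so eligibility for the rate depends on a step the question does not judge.

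The percentage and its interval are the whole primary result, since the plan has no test and no threshold. Protocol 7.2 defends the single arm on the ground that performance and safety results can be set against existing evidence, and the stated purpose is to support marketability in Europe. As planned, a device that prevented some surgeries from being completed could still report 100%.

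**Working it through.** **The plan's own figure.** Protocol 12.8 and SAP 6 give a half-width below 10% at n = 100 and p = 50%. 1.96 × √(0.5 × 0.5 / 100) = 0.098, or 9.8%, which reproduces it. The calculation says nothing about uncompleted surgeries. The enrolment allowance covers only 10% screen failure and 10% loss to follow-up.

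**Inputs.** Definitions come from SAP 2.1, 2.2, 4.3 and 4.3.1; the interval is the exact binomial of SAP 4.3.1. The number of attempted eyes not completed, k, is not in the documents. I assume k = 0 to 5 of 100 attempted eyes.

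**Error in the rate.** Let p be the 'Yes' rate in completed eyes and q the rate in uncompleted eyes. The planned rate is p. The rate in all attempted eyes is [(100 − k)p + kq]/100. The difference is (k/100)(p − q): upward if p > q, downward if q > p, zero if k = 0.

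**Exact limits.** For x 'Yes' of n, the lower limit is the 2.5% quantile of Beta(x, n − x + 1) and the upper limit is the 97.5% quantile of Beta(x + 1, n − x). When x = n, the lower limit is 0.025^(1/n) and the upper limit is 100%.

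**Case A: every uncompleted eye 'No', every completed eye 'Yes' (p = 1, q = 0).**

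| k | Planned (all-implanted) | All attempted | Lower limit overstated by |
|---|---|---|---|
| 0 | 100/100 = 100% (lower 96.38) | 100/100 = 100% (lower 96.38) | 0 |
| 1 | 99/99 = 100% (lower 96.34) | 99/100 = 99.0% (94.55–99.97) | 1.79 points |
| 3 | 97/97 = 100% (lower 96.27) | 97/100 = 97.0% (91.48–99.38) | 4.79 points |
| 5 | 95/95 = 100% (lower 96.19) | 95/100 = 95.0% (88.72–98.36) | 7.47 points |

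If the k eyes come on top of 100 completed eyes, the picture is much the same: 100/103 = 97.1% (91.7–99.4) at k = 3 and 100/105 = 95.2% (89.2–98.4) at k = 5, against a planned 100% (96.4–100).

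**Case B: mixed.** Five uncompleted eyes, 2 'No' and 3 'Yes', all completed eyes 'Yes': 95/95 = 100% (96.2–100) as planned, against 98/100 = 98.0% (93.0–99.8). The overstatement is 2 points.

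**Case C: the reverse.** Five uncompleted eyes all 'Yes', 2 completed eyes 'No': 93/95 = 97.89% (92.60–99.74) as planned, against 98/100 = 98.00% (92.96–99.76). The understatement is 0.1 point.

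**Bounds at k = 5.** The largest upward error is 5p points (q = 0) and the largest downward error is 5(1 − p) points (q = 1). At p = 90% these are 4.5 and 0.5; at p = 50% both are 2.5. The upward bound is the larger for any p above 50%.

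**The case against.** The strongest reply is that little turns on this. The study is a descriptive feasibility study with no decision rule, and the documents name no external benchmark for this particular question. Uncompleted cases would not be hidden: SAP 3 lists them, and adverse events, device deficiencies, secondary interventions and unplanned intraoperative procedures are all reported in the safety set. Eligibility is narrow, so non-completion may be rare or absent. The 5-point and 7.5-point figures need 5 uncompleted eyes, all 'No', with every other eye 'Yes'.

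Much of this stands as a limit on size. The extent of the bias is unknown and may be zero. Its direction is a judgement, because a surgery may stop for reasons unrelated to the device and still be rated 'Yes'. The asymmetry between upward and downward error depends on p being above 50%. It does not rescue the definition: listings and safety tables show the excluded eyes but leave the percentage and its interval unchanged.

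Three narrower points are fair. 'Successful completion' is not defined. On a plain reading, a case finished by other means with an IOL stays in and can be rated 'No', so it adds no bias; a narrower reading would exclude more eyes. The safety set requires contact with the eye, so a failure before contact is still missed. Some protocol text is redacted and the Deviations and Evaluability Plan is not available, so the absence of a wider analysis can be asserted only for the text at hand.

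**Conclusion.** The concern holds. It is certain from the text that the primary rate is conditional on completed surgery with an IOL, and that the plan foresees attempted eyes outside that set. Upward bias is likely, because eyes whose surgery could not be completed are more likely than others to be rated 'No', but it is not guaranteed.

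Under the assumed range of 0 to 5 uncompleted eyes per 100 attempted, the rate is overstated by 0 to 5 points and its lower limit by 0 to 7.5 points in the extreme case. No formal conclusion changes, since none is planned. What changes is the headline estimate and its interval. This should be corrected before data are seen.

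**What to change.** - Compute the primary rate and its exact 95% interval in the existing safety analysis set, using the surgeon's recorded answer.
- State that the questionnaire is completed for every attempted eye, including when surgery is not completed.
- Report how many attempted eyes have no answer, and add a labelled sensitivity analysis counting them as 'No'. The main analysis stays without imputation, as SAP 4.3 plans.
- Keep the all-implanted set as a supportive analysis of the rate and for incision-to-closure time.

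The cost is wording in SAP 2.1, 4.3 and 4.3.1, Protocol 12.2.1 and the Protocol Section 3 summary, plus one sentence on the questionnaire. The protocol wording needs an amendment under Protocol Section 4. The set and the questionnaire are already planned, and sample size and assessments are unchanged. The one downside for the sponsor is that the reported percentage may be slightly less favourable.
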